### **8.2.2. Reporting Serious Adverse Events**

SAEs that occurred at or before Week 52 (EOS visit) or ET visit must be reported to Sponsor or its designated representative via eCRF SAE report form at least within 24 hours of the Investigator becoming aware of the event.

SAEs that occurred after Week 52 (EOS visit) or ET visit and that are considered to be related to the IP must be reported to Sponsor or its designated representative using the paper SAE report form at least within 24 hours of the Investigator becoming aware of the event.

Date and time (wherever possible) of Investigator becoming aware of the SAE will be recorded in the SAE form and source document properly.

In particular, if the SAE is fatal or life-threatening, Sponsor must be notified immediately, irrespective of the extent of available SAE information. This timeframe also applies to additional (follow-up) information that becomes available on previously forwarded SAE reports. Sponsor will then follow expedited reporting procedures according to local and international regulations as appropriate.

The Investigator is obligated to pursue and provide information to Sponsor on all SAEs in accordance with the timeframes for reporting specified above. In addition, Investigator may be requested by Sponsor to obtain specific additional follow-up information in an expedited fashion. In general, this will include a description of the SAE, which should be provided in sufficient detail so as to allow for a complete medical assessment of the case and independent determination of possible causality. Information on other possible causes of the event, such as concomitant medications and illnesses must be provided. In the case of a subject death, a summary of available autopsy findings must be submitted as soon as possible to Sponsor or its designated representative.

All SAEs will be followed until event resolution or stabilisation (for chronic events), if possible, even when a subject is discontinued from IP. For chronic events that does not fully resolve until years later, the outcome should be reported as "resolved with sequelae" as soon

as the event has stabilised or returned to baseline. Follow-up information for the SAE should be actively sought and submitted as the information becomes available.

### **8.3. Adverse Events of Special Interest**

The following AEs in the study eye will be classified as Adverse Events of Special Interests (AESIs) in this study:

- Any case of new onset IOP of > 21 mm Hg that does not respond to treatment, except the transient pressure rise observed within an hour after ITV injection of IP
- Any case of IOP  $\geq$  35 mmHg, at any time, that required treatment
- Any case of intraocular infection such as endophthalmitis
- Any case of intraocular inflammation such as iritis, vitritis and iridocyclitis
- Iatrogenic traumatic cataract
- Arterial thromboembolic events defined as nonfatal stroke, nonfatal myocardial infarction, or vascular death (including deaths of unknown as cause)

### **8.4. Pregnancy**

Any pregnancy, including those of female partners of male subjects treated with the IP, should be reported to the Sponsor. If the female partner of a male subject becomes pregnant, a written informed consent must be obtained from the female partner before collecting any pregnancy-related data. All pregnancies associated with the subject, from the time the subject receives the first ITV injection of IP until either Week 52 (EOS visit) or ET visit, should be reported to the Sponsor. Pregnancy reports should be submitted to the Sponsor within 24 hours from when the Investigator became aware of the pregnancy, using the Pregnancy Report Form.

Although pregnancy is not an AE, all pregnancies must be followed up every 2 months until 6-8 weeks after the outcome of the pregnancy becomes available, unless the subject is lost to follow-up. The pregnancy outcome should be notified to the Sponsor by submitting a follow-up Pregnancy Report Form. If the outcome of the pregnancy meets the SAE criteria then the Investigator should report this case according to the SAE reporting process ([Section 8.2.2.](#)).

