### 4.1. Inclusion Criteria

Subjects must meet all of the following criteria to be eligible for the study:

1. Age  $\geq$  50 years at Screening
2. Newly diagnosed, \*active subfoveal Choroidal Neovascularisation (CNV) lesion secondary to AMD in the study eye

- \* Active CNV indicates presence of leakage and intra- or sub-retinal fluid which should be confirmed by central reading centre during Screening
3. The area of CNV must occupy at least 50% of total lesion in the study eye (confirmed by central reading centre during Screening)
  4. Total lesion area  $\leq$  9.0 Disc Areas (DA) in size (including blood, scars and neovascularisation) in the study eye (confirmed by central reading centre during Screening)
  5. Best Corrected Visual Acuity (BCVA) of 20/40 to 20/200 (letter score of 73 to 34) using original series Early Treatment Diabetic Retinopathy Study (ETDRS) charts or 2702 series Number charts in the study eye at Screening and at Week 0 (Day 1) prior to randomisation
  6. Non-childbearing potential female (e.g., permanently sterilised, postmenopausal [defined as 12 months with no menses without an alternative medical cause prior to Screening]), OR Childbearing potential female subjects or male subjects with their (respectively male or female) partners who agree to use at least two forms of appropriate contraception method that can achieve a failure rate of less than 1% per year (e.g., established use of oral, injected, intravaginal, transdermal or implanted hormonal contraceptive, placement of an intrauterine device or intrauterine hormone-releasing system, bilateral tubal occlusion, vasectomised partner, physical barrier, sexual abstinence) from Screening until 3 months after the last ITV injection of IP
  7. Written informed consent form must be obtained from the subject prior to any study related procedure (If the subject is legal blindness or illiterate, an impartial witness should be present during the entire informed consent discussion)
  8. Willingness and ability to undertake all scheduled visits and assessments

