## **5. TREATMENT AND INVESTIGATIONAL PRODUCT**

### **5.1. Treatment of the Subjects**

#### **5.1.1. Dosing and Treatment Schedule**

Subjects will be administered SB11 or Lucentis® 0.5 mg via ITV into the study eye every 4 weeks up to Week 48 (a total of 13 administrations of IP) unless they are early discontinued from IP.

IP injection will be performed by the Investigator according to delegation of study personnel for this study.

Dosing visits will be allowed within  $\pm 7$  days of the scheduled dosing visit date (except Week 0 (Day 1), visit window not allowed). If a dose of IP is not given within 7 days of the scheduled dosing visit date, the IP should be given within 20 days of the scheduled dosing visit date, but the case will be captured as protocol deviation. Dosing skip is defined when a subject does not receive the IP within 20 days after scheduled dosing visit date.

Next scheduled dosing visit date and visit window should not be altered even though previous dosing is not performed on the exact scheduled dosing visit date (but, the interval between two doses injected into the study eye should be at least 14 days) or previous dosing is skipped.

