### **7.16. End of Study (Visit 16, Week 52 ± 7 days) or Early Termination Visit**

End of study (EOS) or Early Termination (ET) visit is defined as 4 weeks (± 7 days) after the last ITV injection of SB11 or Lucentis®. For ET visit, PK sampling will be excluded from the following procedures.

- NEI VFQ-25 (before dilation of pupil)
- Vital signs (temperature, blood pressure and pulse rate)
- Physical examination (only body weight)
- Blood and urine sampling for clinical laboratory tests
  - Urine samples must be collected before performing FA to avoid false elevation in urine protein values
- Blood sampling for immunogenicity
- Blood sampling for systemic exposure for subjects participating in PK evaluation
- Pregnancy test (serum or urine) at the Investigator's discretion
- Ocular assessments:
  - BCVA examination using original series ETDRS charts or 2702 series Number charts (before dilation of the pupils and FP/FA or OCT assessment)
    - Subject must use the same chart consistently from Screening to Week 52 (EOS visit) or ET visit
  - Slit lamp biomicroscopy
  - Indirect ophthalmoscopy
  - FP & FA (images should be sent to central reading centre)
  - OCT (images should be sent to central reading centre)
  - IOP using Goldmann applanation tonometry
- Adverse event monitoring
- Review of concomitant medication or therapy

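### Section 8.4 sets two different pregnancy reporting periods, and the dated one closes about 9 weeks before the contraception period in inclusion criterion 6 ends

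*Combined protocol and SAP*

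**What the plan says.** Four parts of the protocol bear on this.

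- **Section 8.4, opening sentence.** "Any pregnancy, including those of female partners of male subjects treated with the IP, should be reported to the Sponsor". No start or end date is attached.
- **Section 8.4, third sentence.** Here the reporting period begins with a subject's first dose and is closed by the words "until either Week 52 (EOS visit) or ET visit, should be reported to the Sponsor". This gives a start and an end.
- **Section 4.1, criterion 6 (same in the Synopsis).** Women of childbearing potential, and male subjects with their partners, must use contraception "from Screening until 3 months after the last ITV injection of IP".
- **Section 7.16 (same in footnote 25 to Table 1).** "End of study (EOS) or Early Termination (ET) visit is defined as 4 weeks (± 7 days) after the last ITV injection". Injections run "every 4 weeks up to Week 48 (a total of 13 administrations of IP", so for a completer the last one is at Week 48.

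Section 8.4 also states that pregnancy is not an adverse event. A reported pregnancy is followed every 2 months until 6 to 8 weeks after its outcome is known, and an outcome meeting the seriousness criteria goes into the SAE process.

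**The concern.** Criterion 6 treats the 3 months after the last injection as a time when pregnancy should be avoided. The dated sentence in 8.4 stops asking about pregnancy roughly one third of the way through that time. The opening sentence of 8.4 does not stop at all. A site reading the section meets two scopes, and the more specific one is the shorter.

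What is at stake is safety information. Follow-up to outcome under 8.4 begins only once a pregnancy has been reported. A pregnancy that a site considers outside the period would be neither notified nor followed.

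The lower age limit of 50 reduces the number of possible cases but does not remove them. Criterion 6 still provides for women of childbearing potential. Section 8.4 expressly covers female partners of male subjects, and no entry criterion limits a partner's age.

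**Working it through.** **Inputs**

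- End of contraception period: 3 months after the last injection (4.1, criterion 6). The protocol does not convert months to days, so a range is used below.
- EOS/ET visit: day 28 after the last injection, window day 21 to day 35 (7.16).
- Table 1: Week 48 is D337 and Week 52 is D365.

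**Step 1. The plan's own interval.** 365 − 337 = 28 days, which agrees with the 4 weeks in 7.16.

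**Step 2. The gap.** Gap = (end of contraception period) − (EOS/ET day), both counted from the last injection.

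| 3 months taken as | Visit on day 21 | Visit on day 28 | Visit on day 35 |
|---|---|---|---|
| 84 days (12 weeks) | 63 days (9.0 wk) | 56 days (8.0 wk) | 49 days (7.0 wk) |
| 89 days (shortest calendar) | 68 days (9.7 wk) | 61 days (8.7 wk) | 54 days (7.7 wk) |
| 91.3 days (mean calendar) | 70.3 days (10.0 wk) | 63.3 days (9.0 wk) | 56.3 days (8.0 wk) |
| 92 days (longest calendar) | 71 days (10.1 wk) | 64 days (9.1 wk) | 57 days (8.1 wk) |

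The central figure is 9 weeks, with 8 to 10 weeks across the visit window. Reading 3 months as 12 weeks gives 7 to 9 weeks.

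**Step 3. Share of the period.** 63.3 / 91.3 = 69% of the post-injection contraception period lies after the dated reporting period. This is a share of calendar time, not of risk.

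**Step 4. Early terminators.** The ET visit is also timed from the last injection, so the same gap applies to them.

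**Step 5. Other routes by which a pregnancy in the gap could be captured.**

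- *Related SAE.* "SAEs that occurred after Week 52 (EOS visit) or ET visit and that are considered to be related to the IP must be reported", with no end date (8.2.2), and a congenital anomaly is an SAE (8.2.1). This route covers adverse outcomes judged related. It does not cover a normal pregnancy or an outcome judged unrelated.
- *Scheduled contact.* Section 7 and Table 1 list no visit or call after EOS/ET.
- *Follow-up after ET (4.3).* For subjects who agree, chart review to Week 52 gives BCVA, CST, adverse events and concomitant medication as examples; pregnancy is not among them. For subjects who decline, nothing more is collected.
- *Testing.* The only mandatory test is at Screening (6.3.3); later tests are optional. A pregnancy that began shortly before EOS/ET may be recognised only afterwards, and 8.4 does not say whether onset or awareness decides whether it falls inside the period.

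**The case against.** The strongest reply is that 8.4 already asks for any pregnancy, names female partners, and sets no end date in its opening sentence. Nothing in the section forbids a later report. This stands. A reader might infer from the dated sentence that pregnancies in the interval will certainly go unreported; the documents do not support that. What they show is an undated and a dated instruction side by side, with no statement of which governs. A site may reasonably follow the one with dates.

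The second reply is that the outcome of most concern is covered, because a congenital anomaly judged related to the product stays reportable after EOS/ET. This also stands, but only for that kind of outcome.

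The third reply is that the whole interval should not be described as a time of drug exposure. Section 1.2 gives a vitreous half-life of about 9 days. By first-order decay, 0.5^(28/9) = about 12% of the vitreous amount remains at day 28, and 0.5^(91/9) = about 0.1% at 13 weeks. Predicted peak serum levels (0.79 to 2.90 ng/ml) are below the 11 to 27 ng/ml quoted for 50% inhibition of VEGF activity. A reader might infer that every pregnancy in these weeks would be an exposed one, or that harm is likely; the documents do not show either. They also do not state that reporting must match the contraception period. The point rests on the inconsistency between the protocol's own rules, not on a claim about residual drug.

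Finally, no efficacy endpoint, analysis set or power calculation is touched, and the protocol gives no count of women of childbearing potential or of fertile partners. That is correct and limits the weight of the point.

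**Conclusion.** The point holds as an inconsistency within 8.4, and between 8.4 and criterion 6. The dated reporting period ends about 9 weeks (8 to 10) before the required contraception period does. Pregnancies beginning in that interval may not be captured or followed to outcome if sites apply the dated sentence, except where the outcome is an SAE judged related to the product.

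The figure assumes that 3 months is about 13 weeks and that the EOS/ET visit takes place within its stated window after the last injection. The number of pregnancies affected cannot be estimated from the documents; it is expected to be small. This is an inexpensive improvement to safety reporting that should be made. It has no bearing on the equivalence conclusions, and it implies no view on whether the contraception period itself is the right length.

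**What to change.** Reconcile criterion 6 in Section 4.1 with Section 8.4:

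1. State a single pregnancy reporting period in 8.4, so that the opening and third sentences agree. It should cover at least the contraception period already set in criterion 6. Changing only the end date in the third sentence would leave two scopes in the section.
2. State whether the onset of the pregnancy or the investigator's awareness of it decides whether it is reportable.
3. Direct sites to the existing Pregnancy Report Form for reports after EOS/ET. Section 8.2.2 already provides paper reporting after that visit for related SAEs, so the arrangement has a precedent.

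The cost is an edit to 8.4, with a check that the consent form agrees (its wording was not available for this review), and a few reports for sites to handle after EOS/ET. No extra visit is needed. Without a scheduled contact, late reports would still depend on subjects telling the site, so they should be reminded of this at the EOS/ET visit.

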### **8.5. Independent Data and Safety Monitoring Board**

An independent Data and Safety Monitoring Board (DSMB) will be assigned for this study. The DSMB will consist of external experts (e.g., physician, clinical pharmacologists or biostatisticians) and will review the safety and tolerability data from the study at pre-specified intervals. The details of the safety data and time points for review will be described in the DSMB Charter and in the DSMB Statistical Analysis Plan (SAP).

In addition, an ongoing masked review of AEs, including clinical laboratory data will be continuously undertaken by the Sponsor medical monitor and pharmacovigilance team.

## 9. STATISTICAL METHODS AND DATA ANALYSIS

Further information on the statistical methods to be used in this study will be provided in the SAP, which will be finalised prior to the database lock for reporting the main CSR.

Statistical analysis and reporting will be performed as follows:

- **Interim safety analysis for independent DSMB meeting:**

A DSMB SAP, describing the methodology and presentation of results and access to results will be prepared as a separate document and included in the DSMB Charter. The safety reports for the DSMB data review meetings will be prepared according to the DSMB SAP.

The statistical analysis will be performed by an independent statistical reporting team and the results will be communicated to the DSMB directly by an independent unmasked statistician.

- **Main CSR:**

The main analysis will take place once all subjects complete the procedures at Week 24, or its corresponding visit. Available efficacy and safety data, pharmacokinetics, and immunogenicity data will be analysed and reported.

At the time of this reporting, a limited number of identified individuals of the Sponsor or CRO will be unmasked for reporting purpose. However, subjects, Investigators, and other study personnel will remain masked throughout the entire study period.

- **Final CSR:**

The final analysis will take place after the last subject completes the procedures at Week 52 or the corresponding visit. All study data will be analysed and reported for final CSR.

### 9.1. Analysis Sets

The following sets will be used for the analyses performed in the study:

- Randomised Set (RAN) consists of all subjects who receive a randomisation number at the randomisation visit.
- Full Analysis Set (FAS) consists of all subjects who are randomised at the randomisation visit. Following the intent-to-treat principle, subjects will be analysed

according to the treatment group they are assigned to at randomisation. However, subjects who do not qualify for randomisation and are inadvertently randomised into the study will be excluded from the FAS, provided these subjects do not receive IP during the study period. The FAS will be the primary analysis set for BCVA

- Per-Protocol Set for BCVA (PPS-BCVA) consists of all FAS subjects who have first two IP injections and complete the procedures at Week 8 without any major protocol deviations that have impact on the BCVA assessment. Major protocol deviations that will lead to exclusion from this set will be pre-defined prior to unmasking the treatment group assignment for analyses.
- Per-Protocol Set for CST (PPS-CST) consists of all FAS subjects who have the first IP injection at Week 0 (Day 1) and complete the procedures at Week 4 without any major protocol deviations that have impact on the CST assessment. This PPS-CST will be the primary analysis set for CST. Major protocol deviations that will lead to exclusion from this set will be pre-defined prior to unmasking the treatment codes for analyses.
- Safety Set (SAF) consists of all subjects who receive at least one IP during the study period after randomisation. Subjects will be analysed according to the IP received.
- Pharmacokinetic Analysis Set (PKS) consists of all subjects in the SAF who participate in PK evaluation at PK Investigational sites (PK subjects) and have at least one PK sample analysed.

## **9.2. Statistical Methods and Analytical Plan**

### **9.2.1. Demographics and Baseline Characteristics**

Subject demographics and baseline characteristics will be summarised by treatment group for the RAN and PKS. Continuous variables (e.g., age, weight, height) will be summarised with descriptive statistics (n, mean, SD, median, minimum, maximum) and categorical variables (e.g., gender, race, ethnicity) will be summarised with frequency and percentage.

Comparison between treatment groups in baseline characteristics will be performed using the chi-square test or F-test as appropriate. The results of these tests will be provided including the p-value only for descriptive purposes and will not be used as a formal basis to determine the factors to be included in primary or secondary efficacy analysis models. If baseline imbalances are detected for any of the factors, additional analyses may be performed to adjust for these baseline differences.

Relevant medical history will be summarised by treatment group for the RAN.

Duration of exposure to IP and number of injections will be summarised by treatment group with descriptive statistics for the SAF. Prior and concomitant medications and significant non-drug therapies will be summarised by treatment group with frequency and percentage.

### **9.2.2. Efficacy**

For US FDA, Korea MFDS or other regulatory agency submissions for those who are in favour of the VA, the primary efficacy analysis will be performed for the FAS with the change from baseline of BCVA at Week 8 using an analysis of covariance model with the baseline BCVA as a covariate and region (or pooled centres) and treatment group as factors. The equivalence in BCVA will be declared if the two-sided 90% Confidence Interval (CI) of the difference in terms of BCVA Least Squares mean (LS mean) changes from baseline at Week 8 between SB11 and Lucentis® lies within the pre-defined equivalence margin of [-3 letters, 3 letters].

For EMA or other regulatory agency submissions for those who are in favour of the anatomical parameter, the primary efficacy analysis will be performed for the per-protocol set (PPS-CST) with the change from baseline of CST at Week 4 using an analysis of covariance model with baseline CST as a covariate and region (or pooled centres) and treatment group as factors. The equivalence in CST will be declared if the two-sided 95% CI of the difference of the CST LS mean changes from baseline in Week 4 between SB11 and Lucentis® lies within the pre-defined equivalence margin of [-36 µm, 36 µm].

No formal adjustment of Type I error rates will be performed.

For the primary analysis with the FAS for BCVA, missing data will be imputed for subjects who drop out for the study prior to the primary analysis time-point. A missing-at-random approach will assume that subjects who withdraw from a study had missing values similar to similar subjects who completed the study in that treatment group. This approach ensures that evidence of lack of equivalence is not diluted when there are missing data. For the components of BCVA, the missing letter will be imputed by multiple imputation method with the assumption of monotone missing pattern and regression method. For the sensitivity analyses, available case analysis and last observation carried forward analysis will be performed.

All other secondary efficacy measurements will be summarised descriptively by treatment group and visit, and analysed using analysis of covariance model for continuous outcomes or Cochran-Mantel-Haenszel method for categorical outcomes unless otherwise specified.

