9. OCT will be performed on the study eye at Screening and prior to ITV injection of IP at each visit until Week 48. OCT will also be performed at any time during the visit at Week 52 (EOS visit) or ET visit. Site staffs who will perform OCT scans in this study must be certified by the central reading centre before study starts. OCT devices registered in an Investigational site should be all from the same manufacture and meet the minimum software requirement, The subject should use the OCT device registered by the central reading centre from Screening to Week 52 (EOS visit) or ET visit. OCT images will be sent to the central reading centre.
10. Visit at Week 4 is the most critical as the visit is for the primary endpoint assessment for EMA or other regulatory agency submissions for those who are in favour of the anatomical parameter. Thus, every effort should be made to adhere to the visit schedule for the subjects.
11. FP/FA will be performed on the both eyes at Screening and those images taken from the both eyes will be sent to the central reading centre. FP/FA will also be performed on the study eye prior to ITV injection of IP at Week 24 and at any time during the visit at Week 52 (EOS visit) or ET visit. Those images taken from the study eye will be sent to the central reading centre. Site staffs who will perform FA/FP in this study must be certified by the central reading centre before study starts. Only FP/FA device certified by central reading centre is allowed to be used in this study. If one or more FP/FA devices are certified in an Investigational site, a subject must use the same FP/FA device consistently from Screening to Week 52 (EOS visit) or ET visit. If any significant change in the posterior pole (i.e., subretinal haemorrhage, macular hole, vitreous haemorrhage or opacity, retinal detachment, etc.) is detected with fundus examination, additional FP and/or FA can be performed at the Investigator's discretion, but the images will not be sent to the central reading centre.

12. Indirect ophthalmoscopy using a standard way (i.e., usually using a head-mounted light source and a 20-30 lens) will be performed on the study eye at Screening and prior to ITV injection of IP and within 15 minutes after ITV injection of IP at each visit until Week 48. Indirect ophthalmoscopy will also be performed at any time during the visit at Week 52 (EOS visit) or ET visit.

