**6.2. Efficacy Assessments**

**6.2.1. Best Corrected Visual Acuity**

VA will be assessed in both the study eye and fellow eye (non-study eye) at Screening and prior to ITV injection of IP at each visit until Week 48. VA will also be assessed in both the study eye and fellow eye (non-study eye) at any time during the visit at Week 52 (EOS visit) or ET visit.

VA will be assessed using original series ETDRS charts or 2702 series Number charts at a starting distance of 4 meters, and then repeated at a distance of 1 meter, if necessary. Subject

must use the same chart consistently from Screening to Week 52 (EOS visit) or ET visit. VA testing must be performed before dilation of pupils and FP/FA and OCT assessment.

VA examiners and VA lanes at Investigational sites must be certified to ensure consistent measurement of BCVA prior to start of study.

A detailed protocol for conducting VA testing and refraction will be provided in the VA Testing Manual.

A decrease in VA of  $\geq 15$  letters from the last assessment of VA should be reported as AEs/ Serious Adverse Events (SAEs) as appropriate.

If the event meets one or more of the following criteria, it should be reported as SAE.

- A decrease in VA of  $\geq 30$  letters from the last assessment of VA
- A decrease in VA to the level of Light Perception or worse

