#### **6.4.2. Optical Coherence Tomography (OCT)**

OCT will be performed on the study eye at Screening and prior to ITV injection of IP at each study visit until Week 48. OCT will also be performed at any time during the visit at Week 52 (EOS visit) or ET visit.

Site staffs who will perform OCT scans in this study must be certified by the central reading centre before study starts.

OCT devices registered in an Investigational site should be all from the same manufacture and meet the minimum software requirement. The subject should use the OCT devices registered by central reading centre during the study period.

All original OCT images will be kept in the Investigational site and copies will be sent to the central reading centre for analysis and archiving. A detailed protocol for OCT image acquisition and transmission will be provided in the Image Handbook.

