### After randomisation

#### ✓ Before ITV injection of IP

- NEI VFQ-25 (prior to dilation of pupil after randomisation)
- Vital signs (temperature, blood pressure and pulse rate)
- Blood sampling for immunogenicity
- Blood sampling for pharmacokinetics for subjects participating in PK evaluation
- Pregnancy test (serum or urine) at the Investigator's discretion
- Ocular assessments:
  - Slit lamp biomicroscopy
  - Indirect ophthalmoscopy
  - OCT (images should be sent to central reading centre)
  - IOP using Goldmann applanation tonometry

- Adverse event monitoring
- Review of concomitant and previous medication or therapy
- ✓ **ITV injection of IP**
  - IP (SB11 or Lucentis®) will be given in the study eye.
- ✓ **After ITV injection of IP**
  - Ocular assessments:
    - Indirect ophthalmoscopy (0-15 min post-dose)
    - IOP using Goldmann applanation tonometry (30-60 min post-dose)
  - Blood sampling for pharmacokinetics for subjects participating in PK evaluation (24 - 72 hours post-dose)
  - Adverse event monitoring

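### Each primary ANCOVA provides for one baseline covariate, though BCVA and OCT are both measured twice before the first injection; adding the Screening value is a small, nearly free gain in precision

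*Combined protocol and SAP*

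**What the plan says.** **The models.** Section 9.2.2 and the synopsis give each primary endpoint its own ANCOVA. The BCVA model for Week 8 is fitted "with the baseline BCVA as a covariate and region (or pooled centres) and treatment group as factors". The CST model for Week 4 is fitted "with baseline CST as a covariate and region (or pooled centres) and treatment group as factors". Each names one baseline value, and no section identifies the visit it comes from.

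**The measurements.** Both outcomes are measured twice before treatment.

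- BCVA: section 6.2.1 states that "VA will be assessed in both the study eye and fellow eye (non-study eye) at Screening and prior to ITV injection of IP". Inclusion criterion 5 in section 4.1 applies the 34-to-73-letter limit "in the study eye at Screening and at Week 0 (Day 1) prior to randomisation".
- OCT: section 6.4.2 states that "OCT will be performed on the study eye at Screening and prior to ITV injection of IP at each study visit until Week 48". Section 7.1 sends the Screening images for central reading. The pre-injection list in section 7.2 does the same at Week 0: "OCT (images should be sent to central reading centre)".

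Section 7.1 allows up to 21 days between Screening and randomisation. In section 7.2 the Week 0 BCVA check comes before randomisation. The Week 0 OCT is listed after randomisation but before the injection.

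**What is deferred.** Section 9 leaves further statistical detail to an SAP, to be finalised before the database lock for the main report. The supplied documents contain no separate SAP text.

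**The concern.** A single visual acuity or OCT reading carries measurement error. When one reading is the covariate, that error stops it from fully explaining differences between subjects at the start, and the unexplained part stays in the residual variance. A second pre-treatment reading recovers some of it. Here the second reading is already collected, and eligibility depends on it, so every eligible subject should have one.

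The BCVA comparison is planned at 80% power against a margin of 3 letters, so even a small narrowing of the interval is worth having if it costs almost nothing.

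The definition matters too. Screening, Week 0 and a mean of the two are all compatible with the text. They give different change scores and somewhat different precision. In an equivalence trial that choice should be fixed before anyone sees treatment codes.

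**Working it through.** **Step 1. Reproduce the plan's figures.** Inputs from section 9.3 and the decision rules in 9.2.2:

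- BCVA: margin 3, true difference 0.5, SD 12.5, 90% CI (one-sided 5% per test).
- CST: margin 36 µm, difference 0, SD 133.3 µm, 95% CI (one-sided 2.5% per test).

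With SE = SD × √(2/n), power = Φ((m − d)/SE − z) + Φ((m + d)/SE − z) − 1.

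- BCVA, 334 per arm: SE = 12.5 × √(2/334) = 0.967, power 80.2%. 334/0.95 gives 352 per arm.
- CST, 290 per arm: SE = 133.3 × √(2/290) = 11.07, power 80.4%. 290/0.90 gives 323 per arm.

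Both agree with the plan, and neither depends on how baseline is defined.

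**Step 2. Model for the second reading (BCVA).** Let T be true acuity at Week 0, with Week 0 = T + error, Screening = T + drift + error, and Week 8 = bT + other variation. The documents give none of the components, so these ranges are assumptions:

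- SD of T: 10 to 11 letters
- test-retest SD (e): 3 to 5 letters
- slope b: 0.8 to 1
- SD of untreated drift between the visits (δ): 0 to 5 letters

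The plan's 12.5 is taken as the raw SD of change, so the part of Week 8 variance unrelated to T is v = 156.25 − (b − 1)²T² − e², with T², e² and δ² denoting variances. The residual variances are:

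- Week 0 only: v + b² / (1/T² + 1/e²)
- Week 0 and Screening: v + b² / (1/T² + 1/e² + 1/(e² + δ²))
- Screening only: v + b² / (1/T² + 1/(e² + δ²))

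**Step 3. Central case** (T 10.5, e 4, b 1, δ 3). Here v = 156.25 − 16 = 140.25.

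- Week 0 only: 140.25 + 13.97 = 154.22 (SD 12.42), power 80.8%.
- Both readings: 140.25 + 8.96 = 149.21 (SD 12.22), power 82.2%.
- Reduction: 1 − 149.21/154.22 = 3.2%, equivalent to about 704 × 0.032 ≈ 23 subjects.

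With b = 0.8 and the rest unchanged, v = 156.25 − 4.41 − 16 = 135.84. The residual variance goes from 144.78 to 141.58, a cut of 2.2%, and power from 83.4% to 84.2%.

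**Step 4. Ends of the range.**

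| T, e, b, δ | Week 0 only | Both | Cut | Power |
|---|---|---|---|---|
| 10, 3, 0.8, 5 | 148.53 | 147.50 | 0.7% | 82.3% to 82.6% |
| 11, 5, 1, 0 | 151.97 | 142.58 | 6.2% | 81.4% to 84.0% |

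As δ grows, 1/(e² + δ²) tends to zero and the gain vanishes.

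**Step 5. Check by another route.** Let r be the correlation of each pre-dose value with the outcome, and ρ the correlation between the two values. The variance ratio for their mean against one value is (1 − 2r²/(1 + ρ)) / (1 − r²). For r 0.4 to 0.7 and ρ 0.8 to 0.95 (assumed), the cut is 0.5% to 10.7%. If Screening correlates with the outcome only through Week 0, the added gain is zero. A simulation that applied the 34-to-73 limit at both visits, under its own assumed SDs, gave 4% to 9%. The order of magnitude is stable, but the exact figure depends on the model.

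**Step 6. Screening alone as baseline.** In the central case the residual variance is 140.25 + 20.38 = 160.63, which is 4.2% above Week 0 alone, with power 79.0%. The worst case in the range (T 11, e 3, b 1, δ 5) is 173.79 against 155.63, or about 12% more.

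**CST.** The documents give no OCT repeatability and no correlation between baseline and Week 4, so no comparable figure can be computed.

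**The case against.** The strongest reply is that nothing here is wrong. ANCOVA on one pre-treatment value is valid, its interval has the right coverage, and the sample sizes reproduce. A baseline definition is ordinary SAP content, and section 9 defers to an SAP that is not supplied. Because baseline is undefined, the text does not even exclude a mean of the two readings. All of this stands. It means the second reading is not provided for in the current text, not that precision is known to be lost.

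The gain is also small, and every driver of it is assumed. With slope 0.8 the central case improves by less than one power point. The 80% planning figure may itself be conservative, since section 9.3 states no allowance for covariate adjustment. If 12.5 is the raw SD of change, the one-baseline ANCOVA already has 80.4% to 84.7% power over the assumed range. With equal variances at the two visits and r = 0.6, it has 88.5%, rising to 90.4% with the second reading. This limits the benefit but does not remove it.

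A reader might infer that the sponsor intends to use Screening as baseline, letting up to 21 days of untreated change into the endpoint. No section says so, and the repeat measurements at Week 0 make that visit the natural choice. The loss in Step 6 is therefore a reason to write the definition down, not a demonstrated defect.

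The Week 0 OCT follows randomisation in section 7.2, which might seem to disqualify it as a covariate. It precedes the injection in a double-masked trial, so it remains a pre-treatment measurement.

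**Conclusion.** The point stands as a low-cost improvement together with a missing definition. Each primary model provides for one unspecified baseline value, while two pre-treatment readings of the same measure are scheduled for every subject.

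For BCVA, using both would cut residual variance by about 0.7% to 6.2%, or 0.3 to 2.6 power points. That rests on assumed values for the spread of true acuity, test-retest error, slope and drift, none of which the documents supply. The gain is close to zero if Screening adds nothing once Week 0 is known. For CST the same reasoning holds in principle, but the size cannot be stated.

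It would be wrong to conclude that the trial is underpowered, that either sample size is miscalculated, or that a fixed amount of precision is being lost on both endpoints. The documents support none of these.

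**What to change.** Before unmasking, make three changes in section 9.2.2, the synopsis and the SAP:

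1. Define baseline for BCVA and CST as the last value before the first injection (Week 0), for both the change score and the first covariate. For any FAS subject who is never injected, name the Week 0 value explicitly.
2. Add the Screening value of the same measure as a second pre-specified covariate in the BCVA and CST primary ANCOVAs.
3. Include the Screening value in the multiple-imputation regression for Week 8 BCVA, so that the imputation model contains every covariate of the analysis model.

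Margins, confidence levels, analysis sets and sample size stay unchanged. The cost is a sentence or two of text and one degree of freedom per model, with no new visits or data. A pre-specified pre-treatment covariate does not bias the randomised comparison. If the sponsor prefers one covariate, item 1 is still needed.
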